
 To determine whether a rapid- or slow-wean intervention among infants receiving an opioid (defined as morphine or methadone) as the primary treatment for neonatal opioid withdrawal syndrome (NOWS) affects maternal well-being and maternal infant attachment at four weeks (\pm 7 days) after discharge 	
 Parent-Reported Outcome Measure Information System (PROMIS) Measures at 1 month after discharge and at 24 months of age Maternal Post Attachment Questionnaire (MPAQ) at one month after discharge

 To determine whether a rapid- or slow-wean intervention among infants receiving an opioid (defined as morphine or methadone) as the primary treatment for neonatal opioid withdrawal syndrome (NOWS) affects growth over the first 24 months of age 	
 Weight (kg), length (cm), head circumference (cm), and weight for length percentile on the World Health Organization (WHO) growth curves. Anthropometric z-scores and BMI-z at 24 months of age

 To determine whether a rapid- or slow-wean intervention among infants receiving an opioid (defined as morphine or methadone) as the primary treatment for neonatal opioid withdrawal syndrome (NOWS) affects infant wellness after discharge and until 24 months of age 	
 Acute/urgent care and/or ER visits (total number of occurrences) (CQ) Readmissions (number of occurrences) (CQ) Death (presence or absence)

 To determine whether a rapid- or slow-wean intervention among infants receiving an opioid (defined as morphine or methadone) as the primary treatment for neonatal opioid withdrawal syndrome (NOWS) affects infant development. 	
 Bayley Scales of Infant and Toddler Development, Fourth Edition (Bayley 4): Cognitive, Language, Motor, at 24 months of age

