hospitalized in the NICU (39). Administration takes approximately 10 minutes and includes a total of 33 questions.

The PROMIS Measures will be administered at 1-month after discharge and again at 24 months of age.

We will briefly assess mother-infant attachment with the Maternal Postnatal Attachment Questionnaire (MPAQ; [40]), a 19-item questionnaire that assesses quality of bonding, absence of hostility, and pleasure in interaction. Higher MPAQ scores reflect higher levels of mother-infant bonding. The MPAQ requires approximately 5 minutes to complete, and researchers have validated the MPAQ among postpartum women with substance abuse problems (41). The MPAQ will be administered at 1-month after discharge.

Caregiver(s) will complete the caregiver questionnaire (CQ) to assess enteral feeding, number of ER visits and/or acute/urgent care visits, and hospital readmissions.

We will assess infant neurobehavioral functioning at 24 months of age using the Brief Infant-Toddler Social and Emotional Assessment (BITSEA). The BITSEA is 42-item parent report screener used to indicate social-emotional/behavioral problems in children 12-36 months (42). It will be administered at the 24-month in-person visit. We chose this measure because it is brief, easy to administer, and has good reliability and validity (43,44).

We will assess infant development with the Bayley Scales of Infant and Toddler Development, Fourth Edition (Bayley-IV): Cognitive, Language, Motor at 24 months of age. The Bayley-IV is recognized internationally as one of the most comprehensive tools to assess developmental outcomes in children. With the Bayley-IV, it is possible to obtain detailed information even from non-verbal children as to their functioning. Children are assessed in the 3 key developmental domains of cognition, language, and motor. Reliability and validity of the previous version of the instrument have been well established (45).

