We will analyze the caregiver questionnaire outcomes and the death outcome using a longitudinal GLMM or GEE model appropriate for the outcome type since the data will be collected at multiple time points after discharge. Count data that tend to have more than 0 or 1 events counted will be analyzed using a Poisson model while binary or count data that rarely goes beyond 1 occurrence will be analyzed using a Logistic model. In case of count data that rarely goes beyond 1 occurrence, this data will be transformed to binary data (occurrence/no occurrence). We will present mean outcome ratios for count data (from Poisson models) and odds ratios for binary data (from logistic models) with respect to the intervention effect as well as 95% CI of the intervention effect. All analyses will be adjusted for repeated measures over time, so that patterns of change for these outcomes over time can be assessed by treatment group.

In addition to time of discharge and 24 months of age, anthropometric outcomes will be measured at birth. We will calculate anthropometric z-scores at each of the three assessment periods for the purpose of analysis based on age and gender specific WHO norms. The approach to analyzing weight is given next.

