• Statistical Hypothesis 11B: To compare the height z-score between rapid- and slow-wean groups regardless of medication used.

H₀: Infants z-scores for heights will not differ between rapid- and slow-wean treatment regardless of medication used.

H_a: Infants z-scores for heights will differ between rapid- and slow-wean treatment regardless of medication used.

• Statistical Hypothesis 11C: To compare the head circumference z-score between rapidand slow-wean groups regardless of medication used.

H₀: Infants z-scores for head circumference will not differ between rapid- and slow-wean treatment regardless of medication used.

H_a: Infants z-scores for head circumference will differ between rapid- and slow-wean treatment regardless of medication used.

- 12) **Research Objective 12**: To assess infant wellness after discharge and initial 24 months of age in each intervention arm, by looking at ER visits, acute care facility visits over time, and at the BITSEA scores.
 - Statistical Hypothesis 12a: To compare the number of ER and acute care facility visits between rapid- and slow- wean groups regardless of medication used.

H₀: The rate of ER and acute care facility visits will not differ over time between rapidand slow-wean groups regardless of medication used

H_a: The rate of ER and acute care facility visits will differ over time between rapid- and slow-wean regardless of medication used

• Statistical Hypothesis 12b: To compare the number of ER and acute care facility visits due to NOWS over time between rapid- and slow- wean groups regardless of medication used.

H₀: The rate of ER and acute care facility visits due to NOWS will not differ over time between rapid- and slow-wean groups regardless of medication used.

H_a: The rate of ER and acute care facility visits due to NOWS will differ over time between rapid- and slow-wean groups regardless of medication used.

 Statistical Hypothesis 12c: To compare the number of hospitalizations after an ER and/or acute care facility visits over time between rapid- and slow- wean groups regardless of medication used.

H₀: The rate of hospitalization after an ER and/or acute care facility visits will not differ over time between rapid- and slow-wean groups regardless of medication used.

H_a: The rate of hospitalization after an ER and/or acute care facility visits will differ over time between rapid- and slow-wean groups regardless of medication used.

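### The SAP does not carry over two of the three infant-wellness endpoints as the protocol defines them: readmission is narrowed to admissions after an ER or acute visit, and death after discharge has no specified analysis

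*SAP*

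**What the plan says.** **Protocol.** Table 1 in section 1.7 lists three endpoints under infant wellness after discharge:

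- "Acute/urgent care and/or ER visits (total number of occurrences) (CQ"
- "Readmissions (number of occurrences) (CQ"
- "Death (presence or absence"

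The readmission endpoint carries no condition on how the infant came to be admitted. Section 4.2.17 describes the caregiver questionnaire as covering "number of ER visits and/or acute/urgent care visits, and hospital readmissions", so readmissions are named alongside visits and not as a consequence of them. The schedule of activities (Table 3) has death recorded through to 24 months. Section 5.1.5 supplies the analysis: "We will analyze the caregiver questionnaire outcomes and the death outcome using a longitudinal GLMM or GEE model appropriate for the outcome type".

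**SAP.** Objective 12 in section 2.2.1 assesses wellness "by looking at ER visits, acute care facility visits over time, and at the BITSEA scores". Its four hypotheses are visits (12a), visits due to NOWS (12b), hospitalisations (12c) and BITSEA percentiles (12d). Hypothesis 12c reads "To compare the number of hospitalizations after an ER and/or acute care facility visits over time", and its null and alternative repeat the restriction. Section 4.1 gives 12a to 12c a Poisson or negative binomial mixed model. The matching H12 line in section 6.3 mentions only ER and acute visits, recorded as yes/no at times 1 to 4. Death after discharge is not mentioned in any of these places.

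**The concern.** A protocol endpoint should reach the SAP with the same definition, or the SAP should say why it changed. Here the definition of one endpoint changes and another drops out of sight, and the SAP revision history (section 1.3) gives no reason. Version 2.0 of the SAP did revisit follow-up data, adding section 6.6.2, without touching this.

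The outcomes bear on the question a reader will ask about faster weaning. Protocol section 3.3.2 itself notes that stopping medication too early may leave NOWS incompletely treated and make the move home harder. If the analyst follows 12c as written, the reported hospitalisation count will not be the endpoint the protocol promised. If a child dies after discharge, the SAP gives no instruction for comparing deaths by arm, and none for handling that child's shortened follow-up in the visit and hospitalisation counts.

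**Working it through.** No arithmetic applies: neither document gives an event rate, sample size or power for readmission or death. The check is an item-by-item comparison of the protocol endpoints with every place in the SAP where they could appear.

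| Protocol endpoint (Table 1) | SAP hypothesis (2.2.1) | SAP model (4.1) | SAP outcome list (6.2, 6.3) | SAP display (6.8) |
|---|---|---|---|---|
| ER/urgent-care visits, count | 12a (12b for the NOWS-related subset) | Poisson or negative binomial GLMM | Listed in 6.3, as yes/no | Model-result tables possible |
| Readmissions, count, any route | 12c, only those after an ER/acute visit | Poisson or negative binomial GLMM | Not listed | Model-result tables possible |
| Death to 24 months, present/absent | None | None | None | None named |

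The tally is one carried over, one narrowed and one with no specified analysis: 1 + 1 + 1 = 3.

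**Readmission.** Let A be the readmissions that follow an ER or acute visit and B those that do not, such as direct admissions. The protocol endpoint is A + B. Hypothesis 12c counts A. The shortfall is B, a share B/(A + B) of the endpoint. Neither A nor B can be found in or derived from the documents, so the share cannot be given.

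**Death.** Two named displays might seem to cover it.

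- Table 4 covers adverse and serious adverse events. Protocol section 4.2.12 ends adverse-event assessment at hospital discharge, and the schedule of activities stops serious adverse event monitoring at the same point.
- Table 6 covers in-hospital status by its title.

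Both can show a death before discharge. Neither is specified to show deaths from discharge to 24 months.

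**Follow-up time.** The general model in SAP section 6.4.1 has no follow-up-time term. Section 6.6.2 treats missing follow-up as dropout and does not separate death from it. The SAP is therefore silent on how a child who dies contributes to 12a to 12c.

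**Internal consistency of H12.** Section 4.1 models counts, while section 6.3 describes a yes/no outcome at four times. Protocol section 4.2.17 schedules the questionnaires at five: 1 month after discharge, then 6, 12, 18 and 24 months of age. Protocol 5.1.5 does allow counts to be reduced to yes/no when more than one occurrence is rare, but the SAP does not state that rule.

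**Version check.** The SAP cites protocol version 10, and the protocol supplied is version 11. The log of changes between them lists only face-page items, so a changed endpoint definition does not explain the difference.

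**The case against.** The strongest reply is that nothing has been withdrawn. Protocol 5.1.5 still plans a GLMM or GEE for the questionnaire outcomes and for death, the SAP names the protocol it serves, and the list in SAP 6.3 is expressly open-ended. Hypothesis 12c does analyse hospitalisations. This stands, and it limits the point. A reader might infer that readmission and death will not be analysed at all; the documents do not support that. They support only that the SAP narrows one and specifies nothing for the other. But section 3 of the SAP says it details the analyses for the objectives listed above it, and death is not among them.

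A reader might also infer that the restricted count would be biased between arms because families in one arm reach hospital by a different route. Nothing in the documents suggests this: randomisation is within hospital, and parents, clinicians and research staff are blinded. Incomplete capture is a fair criticism; capture that depends on arm is speculation. Likewise, no percentage of missed events or loss of power can be defended from the documents.

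On importance, the designated safety outcome is Secondary Outcome 6. Wellness is Secondary Outcome 11, among the other secondary outcomes, and SAP 6.4.4 calls every analysis other than the primary exploratory. Hypothesis 12b also addresses post-discharge withdrawal directly. All of this is correct. It lowers the stakes but does not remove the mismatch in definition.

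Finally, the questionnaire itself is not in the documents; protocol section 9 gives form titles only. If the form records admissions only as a follow-on to a visit, an any-route count might not be recoverable. Protocol 4.2.17 and SAP 3.2 both list hospital admissions separately from ER visits, which points the other way.

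**Conclusion.** The point holds as a mismatch between protocol and SAP on secondary outcomes. Two of the three wellness endpoints are not carried over as defined: readmission is reduced to the subset after an ER or acute visit, and death from discharge to 24 months has no specified analysis or display. The effect on results cannot be sized, because no rates are given and the form cannot be seen. The primary analysis is unaffected. The conclusion rests on the wording of the SAP and on adverse-event assessment ending at discharge. It does not rest on any assumed share of direct admissions or on any difference in care-seeking between arms.

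**What to change.** Amend the SAP before the follow-up analysis, which section 3.7 places in July 2026:

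1. Redefine 12c as all hospital readmissions (number of occurrences) by any route, and keep those after an ER or acute visit as a breakdown.
2. Add death to 24 months by arm to Objective 12, section 4.1 and section 6.3, reported as counts with an exact 95% CI for the difference, and name a display for it in section 6.8. An exact method suits a possibly rare outcome and is in keeping with the Fisher fallback already in sections 4.1 and 6.4.2.
3. State that the 12a to 12c count models use follow-up time that ends at death.
4. Reconcile section 6.3 with section 4.1: count or yes/no, with the rule for choosing, and the number of time points.

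If the narrower readmission definition or the omission of death was intended, record the departure from the protocol and the reason instead.

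The cost is a small amendment and a little more analysis. No new data collection is needed, provided the questionnaire records readmissions as protocol 4.2.17 describes.

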3.1 Trial design

A pragmatic, randomized, blinded, multicenter trial to compare a rapid-wean intervention (15% decrements from the stabilization dose) to a slow-wean intervention (10% decrements from the stabilization dose) for infants with NOWS. Randomization is stratified by hospital, with the study protocol commencing after NOWS signs have been controlled with an opioid. Weaning pharmacology treatments are either morphine or methadone administered orally.

3.2 Study Intervention and Process

Participating hospitals must provide opioid replacement therapy with either morphine or methadone as the primary drug for treating NOWS. Hospitals may change use of these two opioids during the trial period. The study protocol will commence after NOWS signs have been controlled with an opioid (stabilization) and weaning of pharmacologic treatment is to be started. At or before each 24-hour interval, clinical team members will evaluate and score infants, per hospital practice, for signs of NOWS to determine if the infant will tolerate weaning of the study drug.

- If the infant can tolerate weaning and is in the rapid-wean intervention arm, the clinical team will reduce the study drug by 15% of the stabilization dose. The clinical team will terminate the study drug when the infant can tolerate 25% of the stabilization dose without NOWS signs.
- If the infant can tolerate weaning and is in the slow-wean intervention arm, the clinical team will reduce the study drug by 10% of the stabilization dose. The clinical team will terminate the study drug when the infant can tolerate 20% of the stabilization dose without NOWS signs.
- If infants cannot tolerate weaning in either intervention arm, infants will enter a 12-hour period of study protocol guideline that will mandate either weaning or escalating the study drug by the end of the 12-hour interval. If the clinical team escalates the study drug, infants will receive opioid using the prior step of the assigned intervention arm.

To maintain blinding of study drug dose during the interventions, the volume of the syringe will be constant and equal the volume of the opioid at stabilization. As the clinical team decreases the study drug during the interventions, the pharmacist will add normal saline to keep a constant syringe volume. Only the pharmacy will be aware of the opioid dose. The use of placebo (normal saline without opioid) in the rapid-wean intervention arm will ensure comparable duration of both weaning interventions.

As part of a pragmatic trial, clinical teams will follow hospital practice for other care practices related to NOWS treatment (type of scoring system, threshold to initiate treatment, duration of stabilization, use of second line and third line-drugs, rooming in, breast milk, etc.). After study drug cessation, the clinical team will observe infants in the hospital for at least 48 hours prior to discharge, which is similar to clinical practice. A trained examiner will administer the Neonatal Intensive Care Unit (NICU) Network Neurobehavioral Scale (NNNS) to assess neurobehavioral profiles after infants cease study drug and prior to discharge.

At one month post discharge, primary caregivers will complete the Parent-Reported Outcome Measure Information System (PROMIS) Measures, the Maternal Postnatal Attachment Questionnaire (MPAQ) and a caregiver questionnaire. The site research team will contact the primary caregiver(s) to update contact information and/or complete questionnaires when the infant is 6 months, 12 months, 18 months, and 24 months of age. The questionnaires will assess infant wellness, visits to emergency room facilities, hospitalizations, and caregiver well-being. At 24 months, the infants will be seen during which a, certified developmental specialists, blinded to the intervention, will administer the Bayley Scales of Infant and Toddler Development, Fourth Edition (Bayley-4) to assess infant neurodevelopment. The PROMIS Measures and the Brief Infant Toddler Social Emotional Assessment (BITSEA) will also be administered during the 24-month visit along with measures of growth.

3.3 Randomization

Stratification: Randomization is stratified by hospital. This is critical to minimize the chance of differences between intervention arms in hospital practices, provider practices, and maternal characteristics.

Randomization: After written informed consent or oral consent (written informed consent to be obtained later) was obtained, qualifying infants were randomized to either rapid- or slow-wean intervention. The Neonatal Research Network Data Coordinating Center (NRN DCC) centrally randomize participants. They developed an allocation sequence with randomly varying block sizes, and they implement the sequence through a central process that is available 24 hours each day. The NRN DCC independently randomizes multiple births. Pharmacy personnel of each participating hospital are the only staff with access to group assignment.

3.4 Sample Size

The projected effect size is a 2.0-day difference in the duration of opioid treatment between infants randomized to a rapid-wean intervention and infants randomized to a slow-wean intervention. The sample size was derived by using results from a recently completed trial comparing morphine-treated infants and methadone-treated infants in which the standard

deviation was 6.9 days for the morphine-treated infants and 8.0 days for methadone-treated infants (see protocol for more details). A standard deviation of 6.9 days was used to derive the sample size, anticipating that more infants will be treated with morphine. However, the primary analysis compares treatment regardless of drug used, and sample size was calculated irrespective of the proportion of infants treated with morphine or methadone.

The study will have two intervention arms (rapid-wean and slow-wean) with 251 morphine/methadone treated infants per intervention arm, for a total of 502 morphine/methadone treated infants. This will achieve 90% power to reject the null hypothesis with a significance level of 0.05 using a two-sided two-sample t-test. The null hypothesis will be morphine or methadone treated infants in both arms will have equal means when the population difference in the duration of opioid treatment is 2.0 days with a standard deviation of 6.9 days. Sample size recalculation was performed in July 2022, using a standard deviation of 6.2 based on data from enrolled infants up to June 2022. It was determined that a sample size of 404 is needed to reach 90% power to reject the null hypothesis with a significant level of 0.05 using a two-sided two-sample t-test, and 302 to reach 80% power. We chose this latter number as our target enrollment.

Subsequently, given continued enrollment challenges faced by this trial, the DSMC and NICHD decided to terminate the trial after December 31, 2023.

3.5 Analysis Structure

The main goal of this analysis is to evaluate whether rapid-wean intervention (15% decrements from the stabilization dose) for infants with NOWS will shorten the days on treatment as compared with a slow wean intervention (10% decrements from the stabilization dose). The secondary goals of analysis will be completed to better understand the effect of rapid-wean by specific pharmacologic intervention (morphine vs methadone), proportion of infants with escalation/resumption of opioid during the intervention, and total amount of opioid used among infants in the rapid and slow wean intervention.

3.6 Statistical Interim Analysis and Stopping Guidance

All interim analyses will utilize Bayesian modeling and predictive posterior inference based on neutral, enthusiastic, and skeptical priors.

Safety Interim Analysis

Per protocol, safety will be assessed after 25%, 50%, and 75% of the enrolled infants are medically ready for discharge. At the 25% mark, we only had one infant with non-related seizure. Interim safety analysis was not performed.

Futility and Efficacy Analysis

Per protocol, efficacy and futility will be assessed after 50% of the enrolled infants are medically ready for discharge.

Important implications and recommendation

Due to slow study enrollment, the data safety and monitoring committee (DSMC) met on August 5, 2022. At the end of this meeting, DSMC recommended enrollment into ACT NOW

Weaning to continue until a target date of December 31, 2023. The DSMC will continue to review recruitment and safety data every 6 months. The DSMC will not look at the primary outcome data again until the end of the study.

Based on this decision, no interim analysis was performed after August 5, 2022.

